This model program could serve as an important new advancement for community-based long term care for PWD that addresses unmet patient- and family-centered needs through civic engagement of seniors. It could also serve as an intervention for dementia risk-reduction and brain health if found to be efficacious.

Research Aims

Aim 1: Adapt and refine the MEMORI Corps intervention for a virtual delivery format using iterative user-centered design principles and multiple stakeholder input.

Aim 2: Conduct a pilot, two-arm, randomized controlled trial to evaluate acceptability, feasibility, safety, and preliminary efficacy of the MEMORI Corps intervention (vs. wait list control group) in 60 community-living PLWD and informal caregiver dyads and 36 volunteer companion guides from geographically and demographically diverse regions in Maryland.

Aim 3: Evaluate the feasibility of ascertainment of community-living PWLD, caregiver, and volunteer-level outcomes over time using virtual and telephonic data collection methods.

[figure not shown]
Overview of study design and procedures.

This is a single blind, intention-to-treat, randomized controlled trial design to evaluate the feasibility and efficacy of a 12 week (12-weeks is the primary end point for PWD/CG outcomes), evidence-based, individualized MEMORI Corps program delivered by trained older volunteers (n=36) to community-living PWD/CG dyads (n=60). Eligible PWD/CG dyads will be randomized to the intervention group (n=30), or augmented waitlist control group (n=30). Intervention group PWD/CGs will be matched with a senior volunteer who will routinely engage and guide the PWD through virtual (and in some circumstances in-person) companion-guided MEMORI Corps activity programming for Weeks 1-12 (at least 5 hours per week of direct guidance/ companion engagement). For the wait-list control group PWD/CGs after 12-week wait list period, the control group will receive the MEMORI Corps Companion guided activity the group for weeks 13-24 weeks.

[figure not shown]
Outcome, process, fidelity, and acceptability measures will be collected at BL, 6 weeks, 12 weeks (primary end point), 18 weeks, and 24 weeks. Eligible volunteers (i.e. “Companion Guides”) will be randomized to 12 months of MEMORI Corps active duty (n=18) where they will be matched to three families over the course of a year, or a 6-month augmented waitlist control group (n=18) followed by opportunity to serve 6 months active duty in MEMORI Corps.

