service, each volunteer will be matched to about three different PWD/CG families (only working with one at a time), spending 12 weeks with each one. The remaining 3 months of the service period will be time off (flexible schedule, coordinated with the Volunteer Coordinator at the Alzheimer's Association). In addition to the 5 hours per week volunteers spend with PWD, they will also spend 1 hours per week in a team meeting with peer volunteers (equaling a total of 6 hours per week of active service). Volunteers (when matched to PWD) will receive a monthly stipend of \$200/month (taxable) similar to^{OBJ1OBJ2}. **Augmented wait-list volunteers** will be offered an opportunity for participation in the intervention arm at 6 months. All volunteers will have outcomes assessed by masked evaluators at 6-months (T2) (the main trial endpoint), and 12-months (T3) (Figure 5). *This assessment schedule is consistent with outcome measurement intervals on physical function, cognition, and engagement in Experience Corps trials.* Willing and eligible wait-list volunteers will then cross-over into the intervention arm, and following the same procedures for intake described earlier, will commit to 6 months of MEMORI Corps program active service, with outcomes assessed by masked evaluators at 6-months (T3) post intervention initiation. Volunteers who have successfully completed 12 months of service, and desire to commit to another 12 months of service will be allowed (within the time frame of the study). Time served in the program and number of PWD/CG dyads matched will be tracked for each volunteer. Volunteers will each receive \$20 for each study assessment.

Recruitment, Enrollment and Randomization. PWD/CG dyads (n=60) will be recruited throughout all counties in Maryland and Baltimore City. (catchment area). To ensure we meet our sample size requirements and the study participants from diverse backgrounds and diverse geographic regions, we will use and

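### Full service for both volunteer arms needs about 72 to 90 dyad placements if every wait-list volunteer crosses over, but 60 dyads supply at most 60

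*Combined protocol and SAP*

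**What the plan says.** **Active arm.** Overview of study design and procedures assigns volunteers to "MEMORI Corps active duty (n=18) where they will be matched to three families over the course of a year". Senior volunteer design and procedures (Figure 5) gives the same load, "each volunteer will be matched to about three different PWD/CG families (only working with one at a time), spending 12 weeks with each one", and adds that "The remaining 3 months of the service period will be time off".

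**Wait-list arm.** The Overview describes a "6-month augmented waitlist control group (n=18) followed by opportunity to serve 6 months active duty in MEMORI Corps". The Figure 5 section says that those who are willing and eligible "will commit to 6 months of MEMORI Corps program active service". It gives no number of families for them. Volunteers who finish a year and "desire to commit to another 12 months of service will be allowed", within the study's time frame.

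**Dyads.** The Overview randomises 30 dyads to intervention and 30 to wait-list. Each is matched with one volunteer for a 12-week course. Wait-list dyads have theirs in weeks 13 to 24, again only if willing and eligible (PWD/CG design and procedures, Figure 4).

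**Volunteer analyses.** Secondary outcome variables names volunteer efficacy over 12 months of service. As exploratory work it adds the change in trajectory of wait-list volunteers after crossover, and an analysis pooling the intervention periods of both arms. The Figure 5 section makes 6 months the main volunteer endpoint.

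**Statements that disagree.** The Executive Summary has volunteers take part for 6 months, assessed at 3 and 6 months. Augmented Wait-list Control puts volunteer crossover at 12 months, not 6. Recruitment, Enrollment and Randomization describes four cohorts of 20, or 80 volunteers, against 36 elsewhere.

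**The concern.** A volunteer's exposure is made of dyad courses, so the 60 dyads limit how much service 36 volunteers can receive. The plan considers supply in one direction only. The recruitment section asks whether there will be enough trained volunteers for the dyads, with a 25% reserve, and nowhere asks whether there will be enough dyads for the volunteers. No rule says who is matched first when dyads are short, and second-year extensions draw on the same pool.

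If the described service exceeds what the dyads can supply, some volunteers counted as in service will be unmatched beyond their planned time off. An analysis labelled as 12 months of service, or as a crossover period, would then estimate the effect of a smaller exposure than the one named. A weak result could be misread as lack of benefit, and this pilot is meant to inform a main trial.

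**Working it through.** The plan states no total number of placements, so the check starts from its own figure per volunteer.

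**1. Families per active volunteer.** Twelve months less 3 off is 9 months. At 52.18/12 = 4.35 weeks per month that is 39.1 weeks, and 39.1/12 = 3.26 courses. The stated figure of about three is reproduced.

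**2. Demand.** Let k be the number of families per crossover volunteer. Six months is 26.1 weeks, and 26.1/12 = 2.17, so at most 2 full courses fit. Pro rata to the active arm, k = 1.5. The range of 1 to 2, with all 18 crossing over, is an assumption.

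Demand = 18 × 3 + 18 × k

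**3. Supply.** Let u be the share of wait-list dyads that cross over, which the plan does not state.

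Supply = 30 + 30 × u

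- u = 1: 60
- u = 0.8: 54
- u = 0.5: 45
- u = 0: 30

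**4. Comparison at the maximum supply of 60.**

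| k | Demand | Shortfall | Share deliverable | Active-arm mean if all 18 crossover volunteers are served, (60 − 18k)/18 |
|---|---|---|---|---|
| 1 | 72 | 12 | 83% | 2.33 |
| 1.5 | 81 | 21 | 74% | 1.83 |
| 2 | 90 | 30 | 67% | 1.33 |

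**5. Active arm alone.** It needs 54, so u must be at least (54 − 30)/30 = 0.80, or 24 of 30 wait-list dyads. With u = 1, 60 − 54 = 6 placements remain. That serves 6 of 18 crossover volunteers at one family each, or 3 of 18 at two.

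**6. Main comparison at 6 months.** Only the active arm draws on the pool: 18 × 1 to 18 × 2 = 18 to 36 placements, within 60.

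**7. Sensitivity.**

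- About three read as 2.5: 45 + 18 = 63 to 45 + 36 = 81, still above 60.
- 20% of volunteers lost before any placement: 0.8 × 72 = 57.6 to 0.8 × 90 = 72. The low end fits, but only with all 60 dyads served. If 20% of dyads are lost too, supply is 0.8 × 60 = 48 and the shortfall returns.
- Executive Summary reading, 6 months of service in both arms: 36 × 1 to 36 × 2 = 36 to 72, which may fit.

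**The case against.** The strongest reply is that the randomised exposure is not shown to be out of reach. The active arm's 54 fits within 60, and the 6-month main endpoint needs at most 36. The shortfall appears only when crossover service is added, and that is an offer to willing and eligible volunteers with no stated number of families. If no more than 6 of 18 cross over at one family each, total demand is 60 or less. On the Executive Summary's duration there may be no shortfall at all. The crossover analyses are exploratory, the study is a pilot, and the Figure 5 section already tracks time served and dyads matched for each volunteer.

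All of this stands, and it limits the point. A reader might infer from 72 to 90 against 60 that the volunteer exposure under evaluation cannot be delivered. The documents do not support that: the main comparison can be supplied if dyads arrive in time, and the 12-month active exposure is at risk, not impossible. A reader might also set 60/36 = 1.67 families per volunteer against the three described. That is not like for like, because three applies to the active arm only. The planned mean over all 36 is 72/36 = 2.0 to 90/36 = 2.5, so the loss at full dyad crossover is 17% to 33%.

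The reply does not remove the inconsistency. It relies on low volunteer uptake or high dyad uptake, neither of which the plan states. The six-month reading contradicts the Overview, the Figure 5 section and the secondary analysis. Tracking records a shortfall but does not prevent one.

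**Conclusion.** The point holds in a limited form. The service described for both volunteer arms needs about 72 to 90 placements against at most 60, a best-case shortfall of 12 to 30. This rests on three families per active volunteer, one volunteer and one course per dyad, and all 18 wait-list volunteers crossing over at one or two families each. The last is an assumption.

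If active volunteers are served in full, crossover service fails first, with at most 6 placements left for 18 volunteers. The exploratory crossover and pooled volunteer analyses are then the most affected. The 12-month active exposure also falls short if fewer than 80% of wait-list dyads cross over. The count does not undermine the 6-month main volunteer comparison, given timely dyads, and the dyad primary outcomes are not in question. Because volunteer outcomes are secondary and preliminary, this is a should-fix point.

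**What to change.** 1. Reconcile volunteer duration, wait-list length, families per volunteer and cohort size across the Executive Summary, the Overview, the Figure 5 section, the recruitment section, Augmented Wait-list Control and Secondary outcome variables. Restate the planned volunteer exposure as what 60 dyads can supply, with its range by dyad and volunteer crossover uptake.
2. Add a matching order, subject to the compatibility matching already planned. Randomised active-arm volunteers who have not reached the 6-month endpoint come first, then wait-list volunteers without a placement. Both take precedence over third placements and second-year extensions.
3. Report matched weeks and hours up to the 6- and 12-month assessments, from the tracking already planned, and describe the volunteer effect as that of the exposure delivered.

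The cost is protocol wording and a rule for the volunteer coordinator, with no extra participants. The drawbacks are less flexibility in matching, longer waits for some volunteers for a third family or an extension, and a stated exposure that looks less favourable.

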PWD/CG design and procedures (Figure 4). PWD/CG dyads will be recruited through a multipronged outreach strategy, in partnership with community organizations, as done previously⁹⁵. Referral dyads will complete a phone screen (e.g. explain study and procedures, determine demographic eligibility, confirm a CG, and screen for cognitive impairment/diagnoses). Those eligible, will receive an initial assessment (via telephone, JHU enterprise secure Zoom platform, or in-person—only if absolutely necessary) by study member study team (research interviewers) to obtain informed consent, confirm eligibility, collect information on baseline outcome measures for PWD and CGs (Table 5). PWD/CG dyads will then be randomized (within 2 weeks) to either intervention or augmented waitlist. Intervention dyads will be referred to the Alzheimer’s Association for additional assessments, to create the individual activity plan (measures on Roles/Occupation/Interests, cognitive, physical, sensory, behavioral function, social orientation, daily routines/activities), and will be matched to a trained volunteer using a set of matching characteristics (geography, sex, age, occupation, interests, faith, and/or culture). The activity coordinator and matched volunteer will then jointly introduce the activity plan (e.g., provide a program orientation/rules, basic education, and teaching in use of activities) to PWD/CG dyad and begin implementation (Table 4). The volunteer will then conduct routine, semi-structured companion sessions using the activity plan for the remainder of the 12-week program virtually via Zoom platform or in a hybrid virtual/in-person format (5 hours per week). CGs will receive a written copy of PWD activity plan, and written educational/coaching materials on various topics (bi-weekly). **Augmented waitlist dyads** (control group) will be offered an opportunity for participation in the intervention arm at 12 weeks. Evaluators masked to group allocation will assess all dyads at 6-weeks (T2), and 12-weeks (T3) (the main trial endpoint). This assessment schedule is consistent with outcome measurement intervals on behavioral and caregiver burden in TAP trial. Willing and eligible wait-list dyads will then receive MEMORI Corps Companion-Guided activity programming (weeks 13-24). PWD and CG will each receive \$20 for each study assessment (T1, T2, T3, T4, T5,).

Figure 4. Study Flow and Randomization for PWD/CG

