Primary outcome variable.

Aim 2: Preliminary efficacy on PWD quality of life (QOL) and neuropsychiatric symptoms and caregiver subjective and objective burden and depressive symptoms compared to augmented wait-list control over 12 week intervention. We will fit a longitudinal linear mixed effects model with a random intercept such that $E[Y_{ij}] = \beta_0 + \beta_1 \text{weeks} + \beta_2 \text{weeks}^* \text{treatment}$, and β_2 represents the difference in change in outcome over time between intervention and wait-list PWD/caregivers

Secondary outcome variables.

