Aim 2: Preliminary efficacy on volunteer physical function, cognition, and social and psychological engagement over 12 months of service. We will fit a longitudinal linear mixed effects model with a random intercept, analogous to those used for PWD outcomes but with months as the unit of time, and volunteers as the unit of measure, rather than PWD/caregiver dyad. **Aim 3:** Acceptability and feasibility of implementing the MEMORI Corps program from various stakeholder perspectives (PWD, informal CGs, senior volunteers, volunteer coordinators/supervisors). Analyses for this aim will be descriptive, and will evaluate treatment adherence, delivery, fidelity and program acceptability and satisfaction from the point of view of the PWDs, caregivers, volunteers, and volunteer supervisors. **Exploratory/Secondary Analyses:** Additionally, we will model change in dyads and volunteers randomized to augmented waitlist followed by intervention, to determine if trajectories for outcomes change between the augmented waitlist and intervention periods. We will also combine the intervention period from both study arms and compare baseline and 12-week measures (for PWD/CG) or 6- and 12-month measures (for Volunteers). With regard to PWD outcomes, we will model all-cause transition from home (including death) during the first 12 weeks as a function of treatment assignment, and we will also compare social engagement and utilization of health (ED/inpatient/outpatient, etc.) and community services between the waitlist and intervention groups, and measure change in utilization among the waitlist participants after they receive the intervention. We will examine potential predictors of intervention response including biological variables such as PWD, CG and volunteer sex, dementia severity, CG relationship, by including intervention x time x predictor terms in longitudinal regression models. To explore the relationships between change in PWDs and caregivers, we will fit parallel process models to data from the intervention period.¹⁰⁶ For example, such a model would allow for the joint modeling of both PWD and caregiver QOL, and would allow for the explicit modeling of correlation between the two trajectories.

Statistical plan including sample size justification

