Analytic Plan. Descriptive analyses will be conducted and measures checked for outliers and to ensure that distributional assumptions of the planned analyses are appropriate. If not, analogous non-parametric methods will be used. The outcomes will be primary modeled using mixed effects regression models which, unlike the method of generalized estimating equations (GEE), do not require data to be missing completely at random.¹⁰⁴ These models allow for correlation of outcomes over time within individuals. Clustering at the volunteer level is possible, but since such clusters would be small relative to the total sample size, it is unlikely that such clustering would affect estimation of standard errors or statistical power to detect a treatment effect.¹⁰⁵ All primary analyses will be intent-to-treat, and will be adjusted for the variables used to balance randomization. We will use "per protocol" secondary analyses to estimate the efficacy on outcomes for intervention participants who receive a minimum dose of intervention (defined as at least 5 hours per week for at least 6 weeks or least 30 hours total of companion guided activity programming post randomization) compared to usual care group participants (control group) who remain in the study for at least 12 weeks post randomization. The intention-to-treat analyses will be the primary analytic approach for this trial. To investigate sensitivity to missing values, those with and without missing

values will be compared by background covariates. Tests will be two-sided and p-values <0.05 will be considered significant. Multiple test corrections will be applied as appropriate.

Sample Size Calculations. Using published recommendations for estimation of pilot trial sample size targets, we revised the pilot trial sample size (Aim 2) to a sample size of 30 per arm for persons living with dementia and caregiver dyads (60 total, including a 20% attrition rate) to plan for the future main efficacy trial with 90% power, 2-sided 5% significance and small (0.2) standardized effect sizes on continuous outcomes. For volunteer companion guides, we revised the pilot trial sample size (Aim 2) to a sample size of 18 per arm (36 total, including a 20% attrition rate) to plan for the future main efficacy trial with 90% power, 2-sided 5% significance and medium (0.5) standardized effect sizes on continuous outcomes.

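### The dyad model tests a difference in slopes with only a random intercept, so its standard error can be too small if within-person correlation fades or slopes differ between people

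*Combined protocol and SAP*

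**What the plan says.** Under Study Statistics, Primary outcome variable (Aim 2), the plan states "We will fit a longitudinal linear mixed effects model with a random intercept such that" the expected outcome is an intercept plus β1·weeks plus β2·weeks·treatment. β2 "represents the difference in change in outcome over time between intervention and wait-list PWD/caregivers". The printed formula has no main effect of arm.

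The visit schedule is in PWD/CG design and procedures: after baseline, "Evaluators masked to group allocation will assess all dyads at 6-weeks (T2), and 12-weeks (T3) (the main trial endpoint"). Three visits therefore enter the randomised comparison.

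The Analytic Plan says of the mixed models, "These models allow for correlation of outcomes over time within individuals". It adjusts the primary analyses for the variables used in the minimisation, and adds "Tests will be two-sided and p-values <0.05 will be considered significant" and "Multiple test corrections will be applied as appropriate". It also plans an assumption check: "Descriptive analyses will be conducted and measures checked for outliers and to ensure that distributional assumptions of the planned analyses are appropriate". If that check fails, the plan turns to non-parametric methods.

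Nowhere do the documents mention a random slope, another covariance structure, robust standard errors or small-sample degrees of freedom.

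**The concern.** β2 is a contrast of slopes, so its precision depends on how much one person's change over 12 weeks differs from another's. A random intercept lets people differ in level only. All remaining variation in change is treated as independent visit-to-visit noise with the same variance at each visit. If people truly follow different trajectories, or if baseline and week 12 are less alike than adjacent visits, the model can understate the variance of the slope contrast.

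What would be at stake is the p-value and interval for each dyad outcome: quality of life, neuropsychiatric symptoms, caregiver burden and depressive symptoms. Results with p<0.05 are to be called significant, and the pilot is meant to inform a larger trial. Intervals that are too narrow would make the preliminary signal look firmer than it is.

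**Working it through.** **Inputs from the documents.** Visits at 0, 6 and 12 weeks; 30 dyads per arm; two-sided 5%; mean model with weeks and weeks by treatment. The documents give no standard error, within-person correlation or slope variance, so there is no plan figure to reproduce.

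**Assumptions.** Baseline SD is 1 and time is scaled t = (0, 0.5, 1). Let w be the within-person correlation before slopes are added (0.7), s the SD of the true 12-week change in baseline SDs, and r the intercept-slope correlation. The true covariance is

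S = w·11′ + (1−w)·I + s²·tt′ + r·s·√w·(1t′ + t1′).

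For serial decay, S has correlations ρ, ρ and ρ².

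**Method.** A random-intercept fit settles on an exchangeable matrix V with the average variance v and average covariance c of S. The model-based variance of β2 comes from (ΣX′V⁻¹X)⁻¹, and its true variance from the sandwich formula with S in the middle. With R = true SE / model SE, the rejection rate under no effect is 2·{1 − Φ(1.96/R)}.

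**Step 1: an arm term added (can be done by hand).** The slope contrast then reduces to the difference between arms in mean change from baseline to week 12.
- Varying slopes: the true variance of the change is 2(1−w) + s² = 0.6 + s². The model uses 2(v−c) = 0.6 + 0.5s². The value of r cancels.
  - s = 0.3: R² = 0.690/0.645 = 1.070, R = 1.034, error 5.8%.
  - s = 0.5: R² = 0.850/0.725 = 1.172, R = 1.083, error 7.0%.
- Serial decay: the true variance is 2(1−ρ²). The model uses 2{1 − (2ρ+ρ²)/3}.
  - ρ = 0.5: R² = 1.500/1.167 = 1.286, R = 1.134, error 8.4%.
  - ρ = 0.8: R² = 0.720/0.507 = 1.421, R = 1.192, error 10.0%.

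**Step 2: the model as printed (no arm term).** Baseline information now enters the estimate, so r matters.

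| Assumed truth | Model SE | True SE | R | Error |
|---|---|---|---|---|
| s = 0 (equal correlation) | 0.1835 | 0.1835 | 1.000 | 5.0% |
| s = 0.3, r = 0 | 0.1896 | 0.1992 | 1.051 | 6.2% |
| s = 0.3, r set so week-12 variance equals baseline | 0.1887 | 0.1941 | 1.029 | 5.7% |
| s = 0.3, r = −0.5 | 0.1869 | 0.1834 | 0.981 | 4.6% |
| s = 0.5, r = 0 | 0.1999 | 0.2245 | 1.123 | 8.1% |
| s = 0.5, r set so week-12 variance equals baseline | 0.1970 | 0.2102 | 1.067 | 6.6% |
| s = 0.5, r = −0.5 | 0.1945 | 0.1978 | 1.017 | 5.4% |
| Serial decay, ρ = 0.5 | 0.2295 | 0.2507 | 1.092 | 7.3% |
| Serial decay, ρ = 0.7 | 0.1990 | 0.2272 | 1.142 | 8.6% |
| Serial decay, ρ = 0.8 | 0.1712 | 0.2000 | 1.168 | 9.3% |

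With w = 0.5 or 0.8 in place of 0.7, the equal-variance rows give 5.4-6.0% at s = 0.3 and 5.9-7.4% at s = 0.5.

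**Step 3: simulation of the printed mean model and of the remedy.** There were 2,500 trials per scenario, with 60 dyads, 10% lost before week 6 and another 10% before week 12 completely at random. Three balancing covariates were minimised on and adjusted for, and models were fitted by REML. The Monte Carlo SE is about 0.45 points at 5%.

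| Assumed truth | Random intercept, normal reference | Unstructured, Kenward-Roger |
|---|---|---|
| s = 0 | 5.8% | 5.6% |
| s = 0.3, r = 0 | 6.9% | 5.3% |
| s = 0.3, r = −0.5 | 5.4% | 5.7% |
| s = 0.5, r = 0 | 8.6% | 4.6% |
| s = 0.5, equal variance | 7.4% | 5.6% |
| s = 0.5, r = −0.5 | 5.1% | 4.6% |
| Serial decay, ρ = 0.8 | 10.6% | 5.5% |

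Part of the 5.8% at s = 0 comes from the normal reference, so the first column should be read against that value. Small-sample degrees of freedom alone are not enough: a random intercept with Kenward-Roger still gave 8.1% (s = 0.5, r = 0) and 10.2% (serial decay). Nor is an unstructured covariance without the correction, which gave 6.2-7.5%.

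**The case against.** The strongest reply is that nothing in the documents shows the covariance assumption to be false. A random intercept does allow correlation over time, as the Analytic Plan says, and 12 weeks is short. At s = 0.3 the simulated excess over the s = 0 value is about one point at most (6.9% against 5.8%), and with a clearly negative intercept-slope correlation the printed model is nominal or slightly conservative. All of that stands, and the concern is therefore conditional.

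A second reply is that the printed formula may be shorthand: it omits the balancing covariates that the Analytic Plan adds, so an arm term may also be intended. That is fair, and it works both ways. An arm term lowers the zero-correlation figures (8.1% becomes 7.0% at s = 0.5). It also removes the conservative exceptions and raises the serial-decay figures.

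A third reply is that this is a pilot, that its size comes from published pilot recommendations and not from this model, and that no go/no-go rule is tied to p<0.05. This limits the consequences but does not make the standard error right.

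Two safeguards in the plan do not answer the point. Distributional checks leading to non-parametric methods do not test or change the covariance structure. Multiplicity corrections act on p-values that already carry the wrong standard error.

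**Conclusion.** The concern holds in conditional form. The primary dyad model fixes a covariance that, for a slope contrast, can give a standard error that is too small, and no other part of the plan relaxes it. At the assumed correlation of 0.7, the nominal 5% error becomes 4.6-6.2% at s = 0.3 and 5.4-8.1% at s = 0.5 as printed, or 5.8% and 7.0% with an arm term. Serial decay with ρ from 0.5 to 0.8 gives 7.3-9.3% as printed and 8.4-10.0% with an arm term. If equal variance and equal correlation hold, there is no problem.

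Three stronger readings are not supported. A reader might infer that the standard error is usually too small; how often depends on the values one chooses to examine, and the documents supply none. A reader might infer error rates well above 10%; under varying slopes at w = 0.7 with r = 0, the printed model passes 10% only when week-12 variance rises by about half, and nothing in the documents points to that. A reader might also carry the point over to the volunteer model, which the plan describes as analogous; no volunteer scenario was calculated, so no claim is made there.

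The practical weight in a pilot is modest, but the correction is cheap enough to be worth making.

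**What to change.** In Study Statistics, Primary outcome variable (Aim 2), keep β2 as the treatment effect and keep the adjustment for the balancing variables. Replace the random intercept with an unstructured covariance across the baseline, 6-week and 12-week visits, fitted by REML, with Kenward-Roger standard errors and degrees of freedom. Name this as the single primary structure. In simulation it held the error at 4.6-5.7% in all eight scenarios run: the seven tabulated and a more extreme one with s = 1.0 and r = 0 (5.2%).

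A correlated random slope with Kenward-Roger controlled the error about as well, but its fits were singular in 54% of simulated trials at s = 0 and 36-39% at s = 0.3. It would therefore need a data-dependent switch to another method, and the error rate of that combined procedure was not examined. The unstructured choice avoids the switch.

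The cost is a sentence or two in the plan, six covariance parameters instead of two, and somewhat wider intervals even when the random-intercept model is right. Width was not measured for the unstructured fit. As a rough guide, the random-slope fit widened the median interval by 5% at s = 0, compared with a random intercept under the same correction. No new data or visits are needed.

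### The plan's only missing-data sensitivity step compares covariates and never re-estimates the treatment effect, so it cannot show whether the effect depends on missing at random

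*Combined protocol and SAP*

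**What the plan says.** Under Primary outcome variable, the outcomes are PWD quality of life and neuropsychiatric symptoms, and caregiver subjective and objective burden and depressive symptoms. The analysis begins: "We will fit a longitudinal linear mixed effects model with a random intercept such that" the coefficient of weeks by treatment carries the effect.

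The Analytic Plan prefers mixed models to GEE because they "do not require data to be missing completely at random". It adds: "All primary analyses will be intent-to-treat, and will be adjusted for the variables used to balance randomization". On missing data it then says: "To investigate sensitivity to missing values, those with and without missing" "values will be compared by background covariates". It gives no other missing-data step, and no rule for acting on what the comparison shows.

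Two other analyses touch on loss to follow-up:

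- The per-protocol analysis selects intervention participants by dose received and controls "who remain in the study for at least 12 weeks post randomization".
- Among the exploratory analyses, "we will model all-cause transition from home (including death) during the first 12 weeks as a function of treatment assignment".

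Neither is presented as a missing-data analysis. Sample Size Calculations allows for loss in the dyad target: "60 total, including a 20% attrition rate".

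**The concern.** A likelihood-based mixed model that does not need data missing completely at random still relies on missing at random, although the plan does not use that term. A sensitivity analysis changes this assumption and shows what happens to the estimate. The planned comparison leaves the estimate untouched. Covariates can look balanced while dropout depends on the unseen outcome, and they can look unbalanced when missing at random holds.

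Informative loss is credible in this trial. The intervention arm is asked for about 5 hours of sessions a week, while controls wait for later access, so reasons for leaving may differ by arm. The plan also treats death and moves from home within 12 weeks as events worth modelling. If the comparison is reported as the sensitivity analysis, readers may take the preliminary efficacy estimates as checked against informative dropout when they have not been.

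**Working it through.** **Inputs from the documents.** 30 dyads per arm; 20% attrition; assessments at baseline, 6 and 12 weeks; random-intercept model with linear weeks and no separate baseline treatment term; two-sided 5% tests; 0.2 SD as the effect named for the future main trial.

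**Inputs assumed.** Within-person correlation 0.5 or 0.7. Losses occur after week 6. In one arm, the unseen 12-week values are worse than the model predicts by δ = 0.25, 0.5 or 1.0 SD. The documents give no such values.

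**The plan's own figure.** The 30 per arm cannot be fully reproduced, because the published recommendation behind it and its base n are not given. It is used here only for the loss rate: 0.20 × 30 = 6 dyads per arm, leaving 24. If the target was instead built as 25 × 1.2 = 30, the loss is 5 of 30 (0.167) and the shifts below become 0.04, 0.08 and 0.17 SD.

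**Step 1: shift in the 12-week difference.** Shift = missing fraction × δ.

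- 0.20 × 0.25 = 0.05 SD
- 0.20 × 0.5 = 0.10 SD
- 0.20 × 1.0 = 0.20 SD

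Against 0.2 SD, these are 25%, 50% and 100%.

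**Step 2: standard error.** Take 24 dyads per arm with three visits and 6 with baseline and week 6 only, unit variance, equal correlation between visits, a common baseline mean and free visit means. The SE comes from the inverse of the sum of X′V⁻¹X over dyads. It is 0.247 SD at correlation 0.5 and 0.203 SD at 0.7.

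**Step 3: type I error when the true effect is zero.** P(|Z + shift/SE| > 1.96):

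| δ (SD) | Shift (SD) | Shift/SE, correlation 0.5 / 0.7 | Type I error |
|---|---|---|---|
| 0.25 | 0.05 | 0.20 / 0.25 | 5.5% / 5.7% |
| 0.5 | 0.10 | 0.40 / 0.49 | 6.9% / 7.8% |
| 1.0 | 0.20 | 0.81 / 0.99 | 12.8% / 16.6% |

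**Step 4: the same under the planned linear-in-weeks model.** The SE is 0.24 or 0.20 SD. The straight line absorbs a little of the week-12 shift, so the bias is about 0.05, 0.09 and 0.18-0.19 SD. Type I error is 5.4-5.7%, 6.7-7.6% and 11.8-15.8%. The figures in Steps 1 and 3 are therefore slight upper values.

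**Step 5: what the covariate comparison would show.** The simulation used 60 dyads, three visits, no true effect, 20% missing at week 12 and 3,000 replicates. It assumed an intraclass correlation of 0.6, log-odds of missingness of 1.5 per SD of outcome in the intervention arm, and a background covariate unrelated to outcome.

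| Missingness depends on | Mean bias (SD) | Comparison significant |
|---|---|---|
| nothing | 0.00 | 4.8% |
| observed week-6 outcome | -0.01 | 5.3% |
| unseen week-12 outcome | -0.10 | 4.9% |

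The comparison behaves alike in all three cases, while the bias does not. Because the covariate was made unrelated to outcome, this is an illustration: it shows that a clean comparison can coexist with bias, not how often it would.

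**The case against.** **What stands.** The primary handling is sound for a pilot: a likelihood model under intent-to-treat, adjusted for the balancing variables. The covariate comparison has real uses. It can speak against missing completely at random and can identify covariates whose inclusion makes missing at random more plausible. The eligibility criteria exclude planned transition from home within 6 months, end-stage disease and crisis situations, partly to limit attrition. The model of transition or death by arm informs on differential loss. That such losses track symptoms or burden is plausible, but the documents do not say it.

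The size is also modest. At 0.25 SD the type I error barely moves. The 95% confidence interval half-width is about 0.40-0.48 SD (1.96 × 0.203 to 1.96 × 0.247), wider than any of these shifts. About six imputed values per arm would drive each shifted estimate, so a long grid across five outcomes would be out of proportion.

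**Stronger readings that the documents do not support.**

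- A reader might infer that the plan should have tested missing at random. No analysis of observed data can do that, and the plan does not claim that its comparison does. What is missing is an analysis that varies the assumption.
- A reader might infer that a biased pilot estimate passes into the main trial or inflates its type I error. Sample Size Calculations already names 0.2 SD for that trial and does not say that the observed pilot effect will replace it. A pilot's bias does not alter the error rate of a separate trial, and nothing says that trial will share the same dropout or missing-data plan.

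None of this supplies an analysis that re-estimates the effect, so the narrower point remains.

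**Conclusion.** The point holds in limited form. The step named for sensitivity to missing values cannot show sensitivity of the treatment effect, and nothing else in the plan varies the missing-at-random assumption. The results rest on 20% loss, correlation of 0.5 to 0.7, and a shift confined to one arm; equal informative dropout in both arms would largely cancel. On those terms the effect is negligible at 0.25 SD, removes about half of a 0.2 SD effect at 0.5 SD, and removes about all of it at 1.0 SD. This is a cheap improvement to a pilot's analysis plan. It does not invalidate the primary analysis.

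**What to change.** 1. Keep the mixed model as the primary analysis.
2. Keep the covariate comparison, described as showing who is missing and as a means of identifying covariates to add to the model. Do not call it a sensitivity analysis.
3. Add, as the sensitivity analysis, delta-adjusted multiple imputation for the primary PWD and caregiver outcomes. Impute under missing at random, then shift the imputed intervention-arm values in the unfavourable direction for each outcome by 0 to 1 SD, for example 0, 0.5 and 1. Refit the same weeks-by-treatment model, so that the result is on the scale of the primary parameter, and report the estimate and confidence interval at each shift.
4. Do not impute PWD outcomes after death. Report missingness by arm and reason: death, transition from home, other withdrawal.

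The cost is about one paragraph in the SAP and a short program. It needs no new visits or participants. The downside is a little more analysis and reporting, estimates that depend on few imputed values, and conclusions that may look less firm.
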